6.3.2 Analysis Populations

Within each tumor type in each cohort the following populations will be defined.

- **Enrolled subjects:** All subjects who signed an informed consent form and were registered into the IVRS.

- **Treated subjects:** All subjects who received at least one dose of nivolumab. This is the primary population for efficacy and safety analyses.
- **Response evaluable subjects:** All treated subjects who have a BOR of CR, PR, SD, Non-CR/Non-PD or PD, and target lesion(s) assessed at baseline, and one of the following: i) at least one on-study timepoint (before sub-sequent therapy) with all baseline target lesion(s) assessed; ii) clinical progression or death before any on-study tumor assesment.
- **Evaluable neoadjuvant subjects:** All treated subjects in neoadjuvant cohorts (N-1, N-2, N-3, N-4) who have available paired tissue samples at screening and Day 29.
- **Pathologic response evaluable subjects:** All treated subject in neoadjuvant cohorts who received study treatment surgery and have known pathological response based on Day 29 TN classification.
- **Outcomes research subjects:** All treated subjects who have an assessment at baseline and at least one post baseline assessment.
- **Pharmacokinetic subjects:** All treated subjects have available serum concentration data.
- **Immunogenicity subjects:** All treated subjects with baseline and at least 1 post baseline immunogenicity assessment.
- **PD-L1 tested subjects:** All subjects who had a tumor tissue sample available for assessment of PD-L1 expression at baseline.
- **Treated PD-L1 tested subjects:** All PD-L1 tested subjects who received at least one dose of study treatment.
- **PD-L1 evaluable subjects:** All treated PD-L1 tested subjects with quantifiable PD-L1 expression.

7 STATISTICAL ANALYSES

7.1 General Methods

Unless otherwise noted, the following subsections describe tabulations of discrete variables, by the frequency and proportion of subjects falling into each category. Percentages given in these tables will be rounded and, therefore, may not always sum to 100%. Continuous variables will be summarized using the mean, standard deviation, median, minimum and maximum values. If a missing category is not being presented in the data display, only those subjects with non-missing values for the parameter being assessed are included in the percentage calculation.

Time to event distribution (e.g. progression free survival, overall survival, time to response, and duration of response) will be estimated using Kaplan Meier techniques. When appropriate, the median along with the corresponding log-log transformed 95% CI will be estimated. Rates at fixed time points will be derived from the Kaplan Meier estimate and corresponding confidence intervals will be derived based on Greenwood formula³ for variance derivation and on log-log transformation applied on the survivor function $S(t)$ ⁴.

Confidence intervals for binomial proportions will be derived using the Clopper-Pearson method⁵.

All analyses will be performed separately for each tumor type upon completion of follow-up for the primary endpoint in each tumor type. Safety analyses will also be performed for each tumor type.

7.2 Study Conduct

7.2.1 Accrual

The following will be presented on the enrolled population:

- Number of subjects accrued by country and investigational site
- Number of subjects accrued by month

7.2.2 Relevant Protocol Deviations

The following programmable deviations will be considered as relevant protocol deviations. Non-programmable relevant eligibility and on-treatment protocol deviations, as well as significant (both programmable and non-programmable) eligibility and on-treatment protocol deviations will be reported through [REDACTED] listings.

At entrance:

- Subjects with baseline ECOG performance status > 1
- Subjects without measurable disease at baseline (only for metastatic cohort)
- Subjects with baseline tumor diagnosis of a tumor type that is not planned in the cohort that the subject was enrolled in.

On-study:

- Subjects receiving anti-cancer therapy (chemotherapy, hormonal therapy, immunotherapy, standard or investigational agents for treatment of cancer) while on study therapy.

A summary table will be produced separately for each tumor type in all treated subjects. A by subject listing will be produced.

7.3 Study Population

7.3.1 Subject Disposition

The total number of subjects enrolled (treated or not) will be presented along with the reason for not being treated. This analysis will be performed on all enrolled population only.

Number of subjects who discontinued study treatment along with corresponding reason will be tabulated. Reason for discontinuation will be derived from subject status CRF page. This analysis will be performed only on all treated population.

A subject list for all treated subjects will be provided showing the subject's enrollment date, first and last dosing date, off study date and reason for going off-study.

7.3.2 Demographics and Baseline Characteristics

Descriptive statistics will be summarized the following baseline characteristics for all treated subjects. All baseline presentations will identify subjects with missing measurements. In

tabulations of categorical variables, percentages are based on subjects with measurements. Listings will also be provided.

- Age group 1 (descriptive statistics); Age categories (< 65, ≥ 65 and < 75, ≥ 75)
- Age group 2 (descriptive statistics): Age categories (18-64, 65-84, ≥ 85)
- Weight (descriptive statistics)
- Gender (Male, Female)
- Race (White, Black, Asian, and Other)
- Region (US/Canada, Europe, Rest of the World)
- ECOG PS (0/1)
- Time from initial disease diagnosis to treatment (< 1 year, 1 - < 2 year, 2 - < 3 year, 3 - < 4 year, 4 - < 5 year, ≥ 5 year)
- Time from initial disease diagnosis to study entry (≤1 year, >1 year)
- All lesions (Investigator Tumor Assessments at Baseline): sites of diseases, number of disease sites per subject
- Target Lesions (Investigator Tumor Assessments at Baseline): Presence of target lesions, site of target lesion, sum of diameters of target lesions.
- Virus status (Positive / Negative) in tumor types (**M-3**) GYN (Cervical, vaginal, and vulva) Carcinoma, (**MC-2a, MC-2b, MC-exp**) Cervical Carcinoma, (**MC-3a, MC-3b**) anogenital HPV associated tumors (vaginal/vulvar/anal canal/penile), (**M-4, MC-4a**) Merkel Cell Carcinoma and (**M-5, MC-5a**) Nasopharyngeal Carcinoma (NPC), SCCHN (**MC-7d**), for which the virus status are tested retrospectively.
- Smoking status (never, current, former, unknown) for SCCHN cohorts **N-1, N-2, M-2, M5, MC-1a, MC-5a, MC-6c, MC-7d**
- Disease location for SCCHN subjects (oral cavity, hypopharynx, oropharynx, larynx, other)
- Disease location for MCC subjects (primary only, lymph nodes only, primary and lymph nodes, visceral)

7.3.3 Medical History

General medical history will be listed by subject.

7.3.4 Prior Therapy

The following will be summarized by tumor type for all treated population:

- Prior therapy (1, 2, 3, ≥ 4)
- Best response to most recent prior regimen (CR/PR vs. SD vs. PD)
- Prior metastatic therapy (yes/no)
- Prior neo-adjuvant therapy (yes/no)
- Prior adjuvant therapy (yes/no)
- Number of prior systemic cancer therapy in metastatic settings (0, 1, 2)
- Time from completion of most recent prior regimen to progression (≤ 3, <3 - ≤6, <6 - ≤12, >12 months)

- Time from completion of most recent prior regimen to study entry (≤ 3 , $<3 - \leq 6$, $<6 - \leq 9$, $<9 - \leq 12$, >12 months)
- Prior surgery related to cancer (yes or no)
- Prior radiotherapy (yes or no)
- Prior/current non-study medication classified by anatomic and therapeutic classes.

Medication will be reported using the generic name. A listing by subject will also be provided.

7.3.5 Baseline Examinations

Percentage of subjects with abnormal baseline physical examination will be tabulated by examination criteria and tumor type for all treated subjects.

7.4 Extent of Exposure

The extent of exposure will be characterized according to the number of subjects exposed, and the duration of exposure. Analyses in this section will be performed on all Treated Subjects for each tumor type in different cohorts.

7.4.1 Administration of Study Therapy

The following parameters will be summarized (descriptive statistics) by tumor type:

- Number (%) of treated subjects exposed for specified periods of time such as less than 1 week, 1 week to 1 month, 1 month to 6 months by treatment.
- Number of doses received (summary statistics)
- Cumulative dose
- Relative dose intensity (%) using the following categories: $< 50\%$; $50 - < 70\%$; $70 - < 90\%$; $90 - < 110\%$; $\geq 110\%$.
- Duration of treatment: duration of treatment will be presented using a Kaplan-Meier curve whereby the last dose date will be the event date for subjects who discontinued study therapy. Subjects who are still on study therapy will be censored on their last dose date. Median duration of treatment and associated 95% CI will be provided.
- A by-subject listing of dosing of study medication (record of study medication, infusion details and dose change) and a listing of batch number will be also provided.
- A by-subject listing of extent of exposure (weight, number of doses, date of first and last dose, cumulative dose, duration of treatment, and reason for discontinuation) will be provided.

Table 7.4.1-1: Administration of study therapy: definition of parameters
Nivolumab monotherapy

Nivolumab	
Dosing schedule per protocol	240 mg every 2 weeks
Cumulative Dose	Cum dose (mg) is sum of the doses (mg) administered to a subject during the treatment period.
Duration of treatment	Last dose date - Start dose date +1
Relative Dose Intensity (%)	Cum dose /[(Last dose date - Start dose date + 14) x 240/14] x 100

Nivolumab combined with Ipilimumab: Combo A

	Nivolumab	Ipilimumab
Dosing Schedule per Protocol	3 mg/kg every 2 weeks	1 mg/kg every 6 weeks
Dose	Dose (mg/kg) is defined as Total Dose administered (mg)/Most recent weight (kg). Dose administered in mg at each dosing date and weight are collected on the CRF	Dose (mg/kg) is defined as Total Dose administered (mg)/Most recent weight (kg). Dose administered in mg at each dosing date and weight are collected on the CRF
Cumulative Dose	Cum Dose (mg/kg) is the sum of the doses administered to a subject.	Cum Dose (mg/kg) is the sum of the doses administered to a subject.
Relative Dose Intensity (%)	Cum dose /[(Last dose date - Start dose date + 14) x 3/14] x 100	Cum dose /[(Last dose date - Start dose date + 42) x 1/42] x 100
Duration of Treatment	Last dose date - Start dose date + 1	Last dose date - Start dose date + 1

Nivolumab combined with Ipilimumab: Combo B

	Nivolumab	Ipilimumab
Dosing Schedule per Protocol	1 mg/kg every 3 weeks for 4 doses followed by 240 mg every 2 weeks	3 mg/kg every 3 weeks for 4 doses
Dose	Dose (mg) is defined as Total Dose administered (mg). Dose administered in mg at each dosing date is collected on the CRF	Dose (mg/kg) is defined as Total Dose administered (mg)/Most recent weight (kg). Dose administered in mg at each dosing date and weight are collected on the CRF
Cumulative Dose	Cum Dose (mg) is the sum of the doses administered to a subject.	Cum Dose (mg/kg) is the sum of the doses administered to a subject.
Cycle Duration _(i) (wk)	(Dose date _(i+1) - Dose date _(i))/7	N/A

Nivolumab combined with Ipilimumab: Combo B

	Nivolumab	Ipilimumab
	For the last dose N, if N<=4, cycle duration (N) (wk)=3; if N >4, cycle duration (N) (wk)=2.	
Cycle Intensity _(i) (mg/kg/wk)	Dose _(i) /Cycle Duration _(i)	N/A
Relative Cycle Intensity (i) (%)	(Cycle Intensity _(i) /intended dose per week) * 100	N/A
Relative Dose Intensity (%)	Sum of all Relative Cycle Intensities divided by N	Cum dose /[(Last dose date - Start dose date + 21) x 3/21] x 100
Duration of Treatment	Last dose date - Start dose date + 1	Last dose date - Start dose date + 1

Volume infused, volume prepared, and weight are collected on the CRF. Nominal nivolumab dose collected in IVRS. $i = 1, 2, \dots, N$, where N = number of infusions. Cycle Duration (N) = 3 weeks for nominal 1 mg/kg nivolumab doses for first 4 doses and 2 weeks for nominal 240 mg after 4th dose. Intended dose per week is xx mg (0.33 mg/kg times subject's weight in kg) for nominal 1 mg/kg nivolumab doses in the first 4 doses and 120 mg for nominal 240 mg nivolumab doses after 4th dose.

Nivolumab combined with BMS-986016: Combo C

	Nivolumab	BMS-986016
Dosing Schedule per Protocol	240 mg every 2 weeks	80 mg every 2 weeks
Dose	Dose (mg) is defined as Total Dose administered (mg). Dose administered in mg at each dosing date is collected on the CRF	Dose (mg) is defined as Total Dose administered (mg). Dose administered in mg at each dosing date is collected on the CRF
Cumulative Dose	Cum Dose (mg) is the sum of the doses administered to a subject.	Cum Dose (mg) is the sum of the doses administered to a subject.
Relative Dose Intensity (%)	Cum dose /[(Last dose date - Start dose date + 14) x 240/14] x 100	Cum dose /[(Last dose date - Start dose date + 14) x 80/14] x 100
Duration of Treatment	Last dose date - Start dose date + 1	Last dose date - Start dose date + 1

Nivolumab combined with Daratumumab: Combo D

	Nivolumab	Daratumumab
Dosing Schedule per Protocol	240 mg q2 weeks (starting at Week 3); 480 mg q4 weeks starting at Week 25	16 mg/kg q1 week (Weeks 1-8), q2 weeks (Weeks 9-24); q4 weeks starting at Week 25
Dose	Dose (mg) is defined as Total Dose administered (mg). Dose administered in mg at each dosing date is collected on the CRF	Dose (mg/kg) is defined as Total Dose administered (mg)/Most recent weight (kg). Dose administered in mg at each dosing date and weight are collected on the CRF

Nivolumab combined with Daratumumab: Combo D

	Nivolumab	Daratumumab
Cumulative Dose	Cum Dose (mg) is the sum of the doses administered to a subject.	Cum Dose (mg/kg) is the sum of the doses administered to a subject.
Cycle Duration _(i) (wk)	(Dose date _(i+1) - Dose date _(i))/7 For the last dose N, if N≤11, cycle duration (N) (wk)=2; if N>11, cycle duration (N) (wk)=4.	(Dose date _(i+1) - Dose date _(i))/7 For the last dose N, if N≤8, cycle duration (N) (wk)=1; if 16≥N>8, cycle duration (N) (wk)=2; if N>16, cycle duration (N) (wk)=4.
Cycle Intensity _(i) (mg/kg/wk)	Dose _(i) /Cycle Duration _(i)	Dose _(i) /Cycle Duration _(i)
Relative Cycle Intensity (i) (%)	(Cycle Intensity _(i) /intended dose per week) * 100	(Cycle Intensity _(i) /intended dose per week) * 100
Relative Dose Intensity (%)	Sum of all Relative Cycle Intensities divided by N	Sum of all Relative Cycle Intensities divided by N
Duration of Treatment	Last dose date - Start dose date + 1	Last dose date - Start dose date + 1

Volume infused, volume prepared, and weight are collected on the CRF. Nominal nivolumab dose collected in IVRS.

For nivolumab, i = 1, 2,...,N, where N = number of infusions. Cycle Duration (N) = 2 weeks for nominal 240 mg nivolumab doses for first 11 doses and 4 weeks for nominal 480 mg after 12th dose. Intended dose per week is 120 mg for nominal 240 mg or nominal 480 mg.

For Daratumumab, i = 1, 2, ..., N, where N = number of infusions. Cycle Duration (N) = 1 week for first 8 doses, 2 weeks for 9th~16th doses and 4 weeks after 17th dose for nominal 16 mg/kg daratumumab doses. Intended dose per week is 16mg/kg for the first 8 doses, 8mg/kg for 9th~16th doses and 4 mg/kg after 17th dose.

7.4.2 Modifications of Study Therapy

7.4.2.1 Dose Delays

Treatment may be delayed for up to a maximum of 6 weeks from the last dose. A dose will be considered as actually delayed if the delay is exceeding 3 days (i.e., greater than or equal to 4 days from scheduled dosing date) for nivolumab and ipilimumab. All studies drugs must be delayed until treatment can resume. Length of delay for study treatment is summarized in Table 7.4.2.1-1. Dose delays will be divided into following categories: 4 - < 8 days, 8 - < 15 days, 15 - < 43, ≥ 43 days. Reason for dose delay will be retrieved from CRF dosing pages.

The following parameters will be summarized by tumor type:

- Number of subjects with at least one dose delayed, number of dose delayed per subject, length of delay and reasons for dose delay

Table 7.4.2.1-1: Length of Dose Delay

Nivolumab monotherapy	
Nivolumab Dose Delay	duration of previous cycle in days - 14

Table 7.4.2.1-1: Length of Dose Delay

Nivolumab monotherapy	
Nivolumab combined with Ipilimumab: Combo A	
Nivolumab Dose Delay	duration of previous cycle in days - 14
Ipilimumab Dose Delay	duration of previous cycle in days - 42
Nivolumab combined with Ipilimumab: Combo B	
Nivolumab Dose Delay	(duration of previous cycle in days - 21) for the first 4 doses (duration of previous cycle in days - 14) starting from the 5th dose
Ipilimumab Dose Delay	(duration of previous cycle in days - 21) for the first 4 doses
Nivolumab combined with BMS-986016: Combo C	
Nivolumab Dose Delay	duration of previous cycle in days - 14
BMS-986016 Dose Delay	duration of previous cycle in days - 14
Nivolumab combined with Daratumumab: Combo D	
Nivolumab Dose Delay	(duration of previous cycle in days - 14) for the first 11 doses (duration of previous cycle in days - 28) starting from the 12th dose
Daratumumab Dose Delay	(duration of previous cycle in days - 7) for first 8 doses, (duration of previous cycle in days - 14) for 9th~16th doses, (duration of previous cycle in days - 28) after 17th doses.

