Subjects who complete the neoadjuvant portion of the study and complete standard of care treatment post-surgery/biopsy who develop unresectable recurrent or metastatic disease within 1 year of surgical resection, or completion of standard of care (whichever is later), may receive treatment with nivolumab monotherapy, if eligible. Eligibility assessments are detailed in [Table 5.1-5](#).

Please refer to the Pharmacy Manual for more detail. There are no pre-medications recommended on the first cycle, **except for Combo D**. All subjects in Combo D will receive pre-infusion and post-infusion medication per the descriptions in [Section 4.7.7](#) of the protocol. If an acute infusion reaction is noted, subjects should be managed according to Section 4.7.7.

Dosing modifications:

There will be no dose modifications allowed for the management of toxicities of individual subjects.

Dosing window:

When nivolumab is administered alone and in combination with BMS-986016 (relatlimab), subjects may be dosed no less than 12 days between doses during Q2 week dosing. For ipilimumab (Combo A), subjects may be dosed within a \pm 1-week window and no less than 5 weeks from the previous dose. For subjects in Combo B, when nivolumab is administered in combination with ipilimumab, subjects may be dosed within a \pm 3-day window and no less than 18 days from the previous dose. A dose given more than 3 days after the intended dose date will be considered a delay, except for subjects receiving ipilimumab in Combo A. A maximum delay of 6 weeks between doses is allowed, except for subjects in the Neoadjuvant cohort.

Daratumumab will be administered at a dose of 16 mg/kg as an IV infusion every week for the 8 doses (-1 and +3 days window is allowed), every two weeks from weeks 9 to 24 (can be delayed up to 1 week) and every four weeks from weeks 25 onwards (can be delayed up to 14 days) until toxicity or disease progression.

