- Ipilimumab should be dosed at the specified interval regardless of any delays in intervening nivolumab doses. However, in order to maintain periodic synchronized dosing of ipilimumab and nivolumab, the dosing days of nivolumab and ipilimumab may be adjusted within the permitted +/- 3 day window, as long as consecutive nivolumab doses are given at least 12 days apart. Ipilimumab may be delayed beyond the 3 day window if needed to synchronize with the next nivolumab dose.
- A dose delay of ipilimumab which results in no ipilimumab dosing for > 12 weeks requires ipilimumab discontinuation, with exceptions as noted in [Section 4.7.6](#).

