4.7.5 Criteria to Resume Dosing

Subjects may resume treatment with study drug when the drug-related AE(s) resolve(s) to Grade 1 or baseline, with the following exceptions:

- Subjects may resume treatment in the presence of Grade 2 fatigue.
- Subjects who have not experienced a Grade 3 drug-related skin AE may resume treatment in the presence of Grade 2 skin toxicity.
- For participants with Grade 2 AST, ALT and/or Total Bilirubin Abnormalities, dosing may resume when laboratory values return to baseline and management with corticosteroids, if needed, is complete.
- Drug-related pulmonary toxicity, diarrhea, or colitis must have resolved to baseline before treatment is resumed. Subjects with persistent Grade 1 pneumonitis after completion of a steroid taper over at least 1 month may be eligible for retreatment if discussed with and approved by the BMS Medical Monitor.
- Subjects who received systemic corticosteroids for management of any drug-related toxicity must be off corticosteroids or have tapered down to an equivalent dose of prednisone ≤ 10 mg/day.

- Drug-related endocrinopathies adequately controlled with only physiologic hormone replacement may resume treatment after consultation with the BMS Medical Monitor. Adrenal insufficiency requires discontinuation regardless of control with hormone replacement.
- Troponin elevations will require the participant to undergo a cardiac evaluation. Following this evaluation, determination of further treatment will be based on the discussion with the BMS medical monitor/designee.
- Dose delay of nivolumab, BMS-986016 and ipilimumab (Combo B), which results in treatment interruption of > 6 weeks requires treatment discontinuation, with exceptions as noted in Section 4.7.6.
- Dose delay of ipilimumab in Combo A, which results in treatment interruption of > 12 weeks requires treatment discontinuation, with exceptions as noted in Section 4.7.6.
- Ipilimumab may not be resumed sooner than 6 weeks (+/- 3 days) after the prior ipilimumab dose for Combo A.
- In general, subjects who meet criteria to resume ipilimumab will also have met criteria to resume nivolumab, so it should be feasible to synchronize dosing of both drugs when resuming ipilimumab. In order to facilitate this, the dosing days of nivolumab and ipilimumab may be adjusted within the permitted +/- 3 day window, as long as consecutive nivolumab doses are given at least 12 days apart.

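### SAP 7.4.2.1 counts Combo A ipilimumab doses given 46 to 49 days after the previous dose as delayed, although Protocol 4.5 allows them and exempts them from the 3-day rule.

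*SAP*

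**What the plan says.** SAP 7.4.2.1 treats a dose as delayed if "the delay is exceeding 3 days (i.e., greater than or equal to 4 days from scheduled dosing date) for nivolumab and ipilimumab". Table 7.4.2.1-1 gives the length of a Combo A ipilimumab delay as the duration of the previous cycle minus 42 days. Delays are grouped as 4 to under 8, 8 to under 15, 15 to under 43, and 43 or more days. By tumor type, the SAP reports the number of subjects with at least one delayed dose, delayed doses per subject, lengths and reasons.

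The dosing-window text of Protocol 4.5 says that a dose given more than 3 days late "will be considered a delay, except for subjects receiving ipilimumab in Combo A". For that drug and regimen it allows a plus or minus "1-week window and no less than 5 weeks from the previous dose". The regimen list in Protocol 4.5 and Table 5.1-3 repeat the 1-week window.

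Two other protocol sections use 3-day wording. Section 4.7.3, on rescheduling, says that "the dosing days of nivolumab and ipilimumab may be adjusted within the permitted +/- 3 day window". Section 4.7.5 says "Ipilimumab may not be resumed sooner than 6 weeks (+/- 3 days) after the prior ipilimumab dose for Combo A".

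**The concern.** Protocol 4.5 is the only place where the protocol defines a delay, and it excludes Combo A ipilimumab from the 3-day rule. The SAP carries over the rule without the exclusion. A site that dosed within the allowed window would then appear in the exposure table as having delayed treatment. Readers use that table to judge how well the combination was tolerated and delivered, so permitted scheduling would be reported alongside real interruptions.

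**Working it through.** **Inputs**
- Planned interval, Combo A ipilimumab: 6 weeks = 42 days (Protocol 4.5; SAP Table 7.4.2.1-1).
- SAP counting threshold: 4 days or more past the scheduled date (SAP 7.4.2.1).
- Protocol window: plus or minus 7 days, never under 35 days (Protocol 4.5).

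**Step 1: where the SAP starts counting.** Delay = interval − 42. Delay ≥ 4 requires an interval ≥ 42 + 4 = 46 days.

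**Step 2: where the protocol window ends.** 42 + 7 = 49 days.

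**Step 3: the overlap.**

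| Interval (days) | SAP delay (days) | Inside protocol window? | SAP counts it as delayed? |
|---|---|---|---|
| 45 | 3 | yes | no |
| 46 | 4 | yes | yes |
| 47 | 5 | yes | yes |
| 48 | 6 | yes | yes |
| 49 | 7 | yes | yes |
| 50 | 8 | no | yes |

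The four conflicting intervals give 4, 5, 6 and 7 days. For this drug and regimen they make up the whole of the 4 to under 8 day category.

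**Step 4: how many people.** SAP Table 5-4 plans 5 × 40 = 200 Combo A subjects. Revised Protocol 06 stopped new randomization in the anogenital cohorts, so the planned total lies between 200 − 40 = 160 (if none of those 40 places had been filled) and 200. Neither document says how often an ipilimumab interval falls at 46 to 49 days, so the number affected cannot be derived.

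**Step 5: rows with a schedule change.** For Combo B nivolumab, Table 7.4.2.1-1 uses "duration of previous cycle in days - 21) for the first 4 doses" and then "duration of previous cycle in days - 14) starting from the 5th dose". Dose 5 is planned 21 days after dose 4, because SAP 7.4.1 has "Cycle Duration (N) = 3 weeks for nominal 1 mg/kg nivolumab doses for first 4 doses". The questionnaire schedule agrees. With dose 4 at Week 10 and dose 5 at Week 13, cycles 8, 12, 16 and 22 fall at Weeks 19, 27, 35 and 47, as in SAP Table 4.3-3; a 14-day gap would give Weeks 18, 26, 34 and 46.

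| On-time dose | If the number means the dose starting the cycle | If it means the dose received |
|---|---|---|
| Combo B nivolumab, dose 5 | 21 − 21 = 0 | 21 − 14 = 7 |
| Combo D nivolumab, dose 12 | 14 − 14 = 0 | 14 − 28 = −14 |

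SAP 7.4.1 defines cycle i as running from dose i to dose i + 1, so it numbers a cycle by the dose that starts it, and it uses the same cut-offs. Under that convention both on-time doses score zero.

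**The case against.** The best defense of the SAP is that the protocol itself uses a 3-day yardstick for ipilimumab in 4.7.3 and 4.7.5. Section 4.7.3 even describes ipilimumab moved beyond 3 days to match nivolumab as being delayed. This shows that the protocol is not uniform, but it does not displace 4.5. The 4.7.3 text concerns synchronizing the two drugs, and the 4.7.5 text sets the earliest date for resuming. Neither defines when a dose is late, and 4.5 does so with an express exemption.

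Two further objections stand in part. Protocol 4.5 gives no replacement threshold, so 50 days is inferred from the window. In addition, ipilimumab and nivolumab are often held or moved together, so the count of subjects with any delay rises only where no other delay is already counted.

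A reader might go further and infer that Table 7.4.2.1-1 is wrong for Combos B and D, giving false 7-day delays at Combo B dose 5 and hiding delays at Combo D dose 12. The documents do not support this as an error. It depends on reading the dose number as the dose received, whereas SAP 7.4.1 numbers cycles by their starting dose. The Combo B ipilimumab row cannot settle the matter: four doses have three 21-day intervals on either reading. Nor is daratumumab dose 17 without a rule, since SAP 7.4.1 pairs the same loose phrase with a 4-week cycle for N above 16. Combo D treatment had in any case been terminated under Revised Protocol 06.

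**Conclusion.** The point holds for Combo A ipilimumab. Doses at 46 to 49 days are within the protocol's window and exempt from its 3-day rule, yet the SAP counts them as delays of 4 to 7 days. This inflates the Combo A counts of delayed doses and, to a lesser extent, of subjects with at least one delay.

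The conclusion rests on Protocol 4.5 being the governing definition and on its exemption covering ipilimumab doses, with Combo A nivolumab left under the 3-day rule. The wording at schedule changes in Table 7.4.2.1-1 is ambiguous, not shown to be wrong.

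The matter is minor. It affects one descriptive exposure table. If the length categories are shown by drug, the permitted doses can be identified afterwards. Adverse events leading to dose delay have their own output (SAP 7.6.4). Objective response rate, the other efficacy analyses and the adverse event analyses do not use this rule.

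**What to change.** In SAP 7.4.2.1, add that Combo A ipilimumab counts as delayed only when the interval exceeds the 1-week window, that is, at 50 days or more. Keep the 4-day threshold for nivolumab and for Combo B ipilimumab.

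Optionally, state in Table 7.4.2.1-1 that the dose number is that of the dose starting the cycle, as in SAP 7.4.1, so that the length subtracted is that of the cycle ending at the dose:
- Combo B nivolumab: 21 days for doses 2 to 5, 14 days from dose 6.
- Combo D nivolumab: 14 days for doses 2 to 12, 28 days from dose 13.

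The cost is one programming condition and, if wanted, one clarifying sentence. No new data are needed.
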